The Revised Photographic Wound Assessment Tool (RevPWAT) is an assessment tool based on the Bates-Jensen Wound Assessment Tool (formerly known as the Pressure Sore Status Tool) for assessments based on photographs of wounds rather than bedside assessments (Thompson, et al., 2013). This outcome measure has been chosen as it does not require the assessors to be at the bedside of the participants, thus blinding them from the allocated mattresses. Blinding assessors from allocated mattresses has been problematic for many of the studies in the literature as the mattresses have visible differences. Thompson, et al. (2013) tested the RevPWAT for reliability and found a strong correlation between bedside assessments and assessments from photographs (intraclass correlation coefficient of 0.89). See Appendices A and B for the assessment tool and instructions on how to score it.

DELIVERY AND FREQUENCY: Photographs for this assessment tool will be taken by clinicians at each wound care session to measure the progression of wound healing and will be scored by assessors blinded to allocated treatment group.

Secondary - Subjective Factors of Pressure Mattresses

Research has shown that there is a strong correlation between non-use of assistive technology and user dissatisfaction, with some of the factors relating to comfort and ease of use (Federici & Borsci, 2011). Regarding pressure mattresses, this means that equipment abandonment will be more likely if the client does not find the mattress comfortable or struggles with moving on it. These subjective measures are considered just as important as wound healing time and so will be measured through surveys provided approximately one week after mattress provision, utilising a Likert scale. The following factors will be included in the survey:

- participants' perceptions of the allocated mattress positives and negatives
- perceived change in sleep habits including:
 - time spent in bed
 - frequency of repositioning
 - sleep position
- comfort of the mattress, including changes in pain levels (see Pain Scale below)
- ease of transfers
- ease of use, including any troubleshooting they have needed to do to date

DELIVERY AND FREQUENCY: This survey will be completed at baseline and then again approximately 1-2 weeks after mattress provision. It will be completed by the participants and facilitated by the primary researcher.

Secondary - Pain Scale using 10-point Scale (Richards, 2015)

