Mattresses that have dual-functionality are excluded. This may be the ability to switch between static and alternating, such as Talley Quattro or Arjo Duo2; or mattresses that use combined static and alternating functionality, such as Curocell Cirrus or Talley Quattro Fusion. Although these mattresses may have clinical applicability in a community setting, their use during the study could confound results, particularly if they are not used as allocated, for example switched to alternating when the participant has been allocated to the static treatment group.

Cushions

To ensure that changes in pressure injuries are due to the mattress and not impacted by time spent sitting out of bed, all participants will be provided with the same air pressure cushion. Air cushions have been shown to have the lowest interface pressure, along with water cushions (Defloor & Grypdonck, 2000). As there are not many water cushions commercially available, an air cushion will be used (high profile ROHO cushion). These cushions are commonly prescribed for people at high risk of developing pressure injuries and so will be familiar to the treating clinicians should any trouble-shooting be required.

Wound Care

Wound care will be provided to the participants as per the current practice for Community Care Nursing, ACT Health. This includes the use of best-practice methods, such as Mepilex range as wound dressing with foam or cavity fillers as needed. Frequency of wound care days will vary depending on the stage of healing. Generally for Grade 2 wounds, wound care occurs every second day, reducing quickly to twice a week, then once per week. Once the wound reaches the stage of visits once per week the wound is considered almost healed as per the RevPWAT (score <2) and thus endpoint for the study.

Data Collection

Participants will be individually coded to prevent identification by assessors and by primary investigator when collecting survey data. Data will be kept in a limited-access folder on secure ACT Health servers behind ACT Health firewalls.

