The methodology will be piloted prior to commencement of the full study to ensure that all components are feasible in practice. From a snapshot taken of the services over a period of 4 months, it is anticipated that intake will be an average of one participant a week so the methodology will be piloted for approximately 8-12 weeks (until endpoint is reached for four participants). It is anticipated that using this same average of intake that data collection for the primary study will take approximately 24 months.

Training of Community Nurses of standardised requirement for taking photographs

To ensure accurate and reliable data is collectable from the photographs a standard operating procedure will be developed. Thompson, et al. (2013) provided tips for ensuring a photograph is taken that is going to reduce the risk of discrepancies between assessors (Information Box 2). In addition to these tips, they also recommend the bedside clinician (ie the person taking the photograph) makes a note of the dressing removed as the dressing type may impact on the surrounding skin or leave residue (Thompson, et al., 2013).

INFORMATION BOX 2: WOUND PHOTOGRAPHY TIPS

- Patient identification number, date and time of when the photograph was taken
- A measurement scale (mm markings preferred) should be placed adjacent to the wound in the same plane as the wound opening.
- Background should be clear of clutter consistent blue or green background is preferred.
- Cleanse, debride and dry the wound area thoroughly before taking photograph
- Use at least a 3.0 megapixel digital camera. Larger than 10 megapixels is not required just results in file storage problems.
- Take photograph close to wound (30-60 cm) and include wound base, all wound edges, sample of periulcer skin (10cm around).
 - Use even consistent, reproducible lighting external ring or extended flash is preferred.
- Avoid shadows and bright spots (open windows, flashlights)
- Take photographs at right angles to the wound opening.
- Stabilise arms or use tripod when taking photograph to avoid shake/movement during photograph.
- Several photographs can be taken at different distances to get "full picture".
- Make notes when taking photographs so subsequent photographs are taken in the same orientation.
- Prevent camera cross contamination follow aseptic technique and disinfection procedure.
- Ensure informed consent is obtained for defined use (time frame and purpose) of photographs.

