b) Provision of support surface will be based on availability.c) Mattress and cushion to be provided and set-up	Primary Researcher ELS Staff Primary Researcher OR ELS Staff
type and ROHO cushion b) Sales Representative to choose mattress from pre-determined list based on mattress type and storeroom availability c) Mattress and ROHO cushion to be provided and set-up	Primary Researcher Sales Representative Primary Researcher OR Sales Representative Primary Researcher
 mattress and cushion, including contact information 12. Wound Management: Wound Management as per standard practice with the following additions: Photograph to be taken as per study recommendations at every dressing change Review participant for changes in function, including skin check for new pressure injuries if new pressure injury has developed this should be photographed and referred to Wound Nurse Practitioner and Primary Researcher for review for ethical impact Repeat Waterlow weekly 	Community Nurses
13. Photograph Management: Photograph will be placed in ACT Health e-note template for photographs in a clinical file with unique identifier only (photograph enlarged for one photograph per page). Document to be saved in PATHFILE (Saved as: "Photograph [Unique identifier] — [date YYMMDD]"), where date is date photo was taken	Community Nurses
	Tissue Viability Nurses
 Data Entry Data from RevPWAT to be entered into data spreadsheet on a weekly basis by Research Team Data from hard-copy surveys will be entered into Qualtrics by Research Team as they are completed (to be entered within one week of survey) 	Primary Researcher Research Team/Admin Support Research Team/Admin Support Primary Researcher

Step	Who
 Participant Completion of study endpoints will be determined by one of the following: e one week following complete healing of the initial pressure injury as determined by the RevPWAT (ie at the point when Community Nursing would be leaving the dressing on for a week – PWAT score of 0 for all subscores except subscore 8, where a score of up to 2 can be permissable) e weeks following the provision of the mattress e removed from the allocated surface – for example by request, move areas, hospitalisation, death, significant deterioration of existing wounds (such as progression to a Grade 3 pressure injury or development of an unstageable pressure injury) 	Information only

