 Collect final data: Photograph initial pressure injury and any remaining pressure injuries as per study recommendations and store as per previous photographs (see Photograph Management) Final Waterlow Risk Assessment Review for changes in function, including a final skin check for additional pressure injuries not previously identified 	Community Nurses
17. Scoring of remaining photographs (see Assessment of wound photograph)	Tissue Viability Nurses
 18. Closure of study: Follow up with participant to ensure ongoing pressure care needs will be met by referral on to the appropriate services Organise for collection of the study mattress and cushion Thank participant for taking part 	Primary Researcher

Data/Secure Folder Management

Data will be kept on ACT Health servers in a secure folder. Access will be limited to the following people with additional restrictions in place:

- Research Team (primary researcher and supervisors, administration support for data entry) (RT)
- Community Nurses providing wound care (CN)
- Tissue Viability Nurses (TVN)

Breakdown of the folder will include the following sub-folders:

- Data Collation documents (additional password protection access for RT only)
 - Mattress allocation document
 - Spreadsheet for RevPWAT
 - o Spreadsheet for demographic data
- Photographs for assessment (this is where the CN will save the de-identified photograph e-note)
 - subfolders for each participant
- Completed Assessments
 - subfolder for each participant which will include
 - Photograph e-notes (TVN or CN responsibility)
 - Completed RevPWATs (TVN responsibility)
 - Completed Waterlows (CN responsibility)
 - Completed surveys (RT responsibility)
 - Completed consent forms (RT responsibility)

- Study Documents (read-and-print-only documents, RT able to modify folder contents)
 - How to Take Wound Photographs
 - How to Complete RevPWAT
 - Study Protocol
 - Information sheets
 - Blank Consent Forms
 - o Blank Baseline Survey
 - o Blank Follow-up Survey

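### Assessors can see photograph dates and earlier scores, so visit spacing set by unblinded nurses can cue the blinded healing score

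*Protocol*

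**What the plan says.** The primary outcome is time to complete healing on the RevPWAT. The Outcome Measures section says that the photographs "will be scored by assessors blinded to allocated treatment group", and gives remote, blinded scoring as the reason for choosing this tool.

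On handling the photographs:

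- **Frequency.** Appendix A, Step 12: "Photograph to be taken as per study recommendations at every dressing change".
- **File name.** Appendix A, Step 13: the name combines the participant's code with a YYMMDD date, "where date is date photo was taken". The e-note itself is to carry the code and no other identifier.
- **Image.** Information Box 2 (photography tips) lists "Patient identification number, date and time of when the photograph was taken".
- **Folders.** Appendix A, Data/Secure Folder Management, has "Photographs for assessment (this is where the CN will save the de-identified photograph e-note", divided by participant. A second folder, Completed Assessments, also has one subfolder per participant. It holds the photograph e-notes, which assessors or community nurses file, and "Completed RevPWATs (TVN responsibility". TVN stands for the Tissue Viability Nurses, who score the photographs (Step 17). Only the Data Collation folder is marked as closed to everyone but the research team.

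On visit spacing, the Wound Care section says: "Frequency of wound care days will vary depending on the stage of healing". It describes visits on alternate days, then two a week, then one. It adds: "Once the wound reaches the stage of visits once per week the wound is considered almost healed as per the RevPWAT (score <2", and makes that the study endpoint. The completion criteria in Appendix A repeat the link by tying RevPWAT healing to the point at which the dressing would stay on for a week.

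**The concern.** Blinding an assessor to allocation protects the outcome only if the score is also independent of people who know the allocation. Here the gap between dates records the treating nurse's opinion of how far the wound has healed. The Discussion of the literature review accepts that treating clinicians cannot be blinded in mattress trials, and under Data Management clinicians document the allocated mattress. An assessor who knows the protocol's equation of weekly dressing with near-healing can read that opinion from the file names before looking at the wound. Earlier scores offer a second anchor.

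At stake is the independence of the primary outcome. The protocol criticises earlier trials on this ground: by its count 78% lacked blinded assessors. A masking gap that costs almost nothing to close is worth closing.

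**Working it through.** No formula applies and the protocol gives no figure to reproduce. The check sets the passages side by side.

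1. **Do the dates reach the assessor?** Step 13 puts the date in the file name. Information Box 2 would put date and time with the image as well. No legible sentence removes either before scoring.
2. **Do the dates show visit spacing?** Yes. Step 12 requires one photograph per dressing change. From the Wound Care section, successive dates would be about 2 days apart, then about 3 to 4 days (7 / 2 = 3.5), then 7 days.
3. **Does spacing carry a healing judgement?** Yes. Wound Care says that frequency follows the stage of healing, and community nurses provide the care.
4. **Is that judgement tied to the endpoint?** Yes, in both Wound Care and the completion criteria. A 7-day gap is the pattern the protocol links with reaching the endpoint.
5. **Are earlier scores within reach?** The assessors file the completed forms in a per-participant subfolder that also holds the photographs, and no stated restriction closes it to them. The same subfolder holds the completed surveys, which ask about the allocated mattress.
6. **Is there room for a cue?** Some, at the margin. The completion criteria require 0 on seven subscores and allow up to 2 on the eighth. On most items, 0 means closed or below 0.3 cm². As printed in Appendix B, however, size scores 0 below 0.3 cm² and 1 from 0.5 cm², so 0.3 to 0.5 cm² has no category. The edges item also allows 0 when edges look indistinct, which is a judgement.
7. **When does the cue arrive?** The photograph taken at the visit where the nurse decides to step down still follows a shorter gap. The weekly gap first appears on the next photograph. It can therefore cue that photograph. It can cue an earlier one only if that is scored after later dates are on file. Step 17 provides for scoring remaining photographs once final data are collected, so this may happen for some.

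Each link from photograph to score stands on the legible text. What it establishes is access to the cue, not its use.

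**The case against.** The strongest reply is that the governing step cannot be read. Step 17 points to a step on assessing the wound photograph, and its text is not legible. The folder section also mentions additional access restrictions without fully specifying them. Masking could be stated in either place. This stands: the point concerns what the visible file names and filing duties allow, and the unread step must be checked before acting.

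Several stronger readings are tempting, and the documents do not support them:

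- **That assessors score in date order with earlier scores in front of them.** YYMMDD names within a participant's folder sort chronologically, but no legible sentence prescribes sequential scoring. New photographs go first to a folder separate from the completed forms.
- **That dates break the allocation blinding.** They do not reveal the mattress, and the allocation document is closed to assessors. The only blinding claimed is to treatment group, so the dates do not contradict that claim.
- **That the effect can be stated in days.** That would need the share of healing calls a cue decides and any difference between arms in step-down timing. The documents give neither. The ruler-based size item and the strict endpoint leave limited room.
- **That the cue pulls the arms together and so favours equivalence.** This requires the same visit schedule in both arms whatever the true healing. Wound Care says the opposite: spacing follows healing. Calls that follow the schedule would then tend to keep a real difference.

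It can also be said that masking dates leaves nurses deciding when photographs exist and leaves weekly dressing in the endpoint wording. That is true. The change removes one cue, not all nurse influence.

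**Conclusion.** The point holds in a limited form. On the legible text, assessors can see visit spacing and earlier scores. The spacing reflects the opinion of nurses who cannot be blinded, and the protocol links weekly spacing with the endpoint. That opinion can therefore cue the primary outcome score when a wound is close to the healing threshold.

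The size and direction of any bias cannot be derived from the document, and none is claimed. The conclusion assumes that the unread photograph-assessment step contains no masking of dates, order or earlier scores. If it does, the remaining task is to align the file-naming and folder rules with it. The case for change rests on the low cost of removing the cue, not on a demonstrated distortion.

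**What to change.** First check the photograph-assessment step for any masking already in place. Then:

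1. Give assessors copies named with a random photograph number, with no date in the file name, e-note or image. Reconcile Information Box 2 with this when the photography operating procedure is written: date and time are still recorded, but not on the assessor's copy.
2. Keep the number-to-date key in the RevPWAT spreadsheet, which already sits in the research-team-only folder. The research team re-attaches dates to find the healing date.
3. Restrict assessor access to the Completed Assessments subfolders once forms are submitted. This also keeps the mattress surveys out of view.
4. Optionally, present each week's photographs in shuffled order across participants. This is a trade-off, not a requirement.

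Scoring can remain ongoing, and wound care and visit frequency are untouched. The cost is a few minutes of administration a week, and assessors lose earlier photographs and scores as a reference.

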- 3. existing Grade 2 pressure injury the majority of pressure injuries managed in the community setting in ACT are Grade 1 or 2 (Lake, 2015).
- 4. have a bed that is appropriate for the test support surfaces
- 5. inability to reposition off the pressure injury—if the participant is able to offload the pressure injury then the support surface is only acting in a preventative manner rather than aiding wound healing.

Considered

Participants with Grade 1 pressure injuries will only be included if they also have a Grade 2 pressure injury, with the Grade 2 pressure injury being considered the primary pressure injury for the purposes of the study. Participants with Grade 1 pressure injuries only will be excluded as Grade 1 pressure injuries do not have any broken skin. It is expected that these will heal much faster and could skew the results with regards to effect size.

Exclusion Criteria

- existing Grade 3, Stage 4, Suspected Deep Tissue Injury or unstageable pressure injury these
 pressure injuries are not seen as frequently in the community setting (Lake, 2015) and have widely
 variable healing times, inclusion will skew the results.
- 2. Participation in the study during a previous episode of care

If accepted against the inclusion and exclusion criteria then prospective participants will be offered opportunity to participate in study – provided with consent paperwork and information package. Upon receipt of consent participant will be randomly allocated to one of three treatment arms.

Outcome Measures

Primary - Time to complete healing based on the Revised Photographic Wound Assessment Tool (Thompson, Gordey, Bowles, Parslow, & Houghton, 2013)

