Appendix B: Revised Photographic Wound Assessment Tool

developed from the Bates-Jensen Wound Assessment Tool (formerly known as PSST) (Thompson, et al., 2013, p 363)

Item	Assessment					
1. Size	0 = wound is closed (skin intact) or nearly closed (<0.3 cm ²) $1 = 0.5 - 2.0 \text{ cm}^2$ $2 = 2.0 - 10.0 \text{ cm}^2$ $3 = 10.0 - 20.0 \text{ cm}^2$ $4 = >20.0 \text{ cm}^2$					
2. Depth	0 = wound is healed (skin intact) or nearly closed (<0.3 cm²) 1 = full thickness 2 = unable to judge because majority of wound base is covered by yellow/black eschar 3 = full thickness involving underlying tissue layers 4 = tendon joint capsule visible/bone present in wound base					
3. Necrotic tissue type	0 = none visible or wound is closed (skin intact) or nearly closed (<0.3 cm²) 1 = majority of necrotic tissue is thin, white/grey or yellow slough 2 = majority of necrotic tissue is thick, adherent white/yellow slough or fibrin 3 = majority of necrotic tissue is white/grey devitalized tissue or eschar 4 = majority of necrotic tissue is hard grey to black eschar					
4. Total amount of necrotic tissue	0 = none visible in open wound or wound is closed (skin intact) or nearly closed (<0.3 cm²) 1 = <25% of wound bed covered 2 = 25% - 50% of wound covered 3 = >50% and <75% of wound covered 4 = 75% or more of wound covered					
5. Granulation tissue type	0 = wound is closed (skin intact) or nearly closed (<0.3 cm²) 1 = majority (>50%) of granulation tissue is healthy-looking (even, bright red appearance) 2 = majority of granulation tissue is unhealthy (eg pale, dull, dusky, hypergranulation) 3 = majority of granulation tissue is damaged, friable, degrading 4 = there is no granulation tissue present in the base of the open wound (all necrotic)					
6. Total amount of granulation tissue	0 = wound is closed (skin intact) or nearly closed (<0.3 cm²) 1 = 75% or more of open wound is covered with granulation tissue 2 = >50% and <75% of open wound is covered with granulation tissue 3 = 25% to 50% of open wound bed is covered with granulation tissue 4 = <25% of wound bed is covered with granulation tissue					

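### Complete healing is fixed by one qualifying RevPWAT score, and the photograph planned for one week later has no stated role in confirming it

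*Protocol*

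**What the plan says.** Under Outcome Measures the primary outcome is "Time to complete healing based on the Revised Photographic Wound Assessment Tool". Photographs come from routine wound care: "Photograph to be taken as per study recommendations at every dressing change" (Appendix A, wound management step).

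Appendix A, in the step on participant completion, ends participation "one week following complete healing of the initial pressure injury as determined by the RevPWAT" and defines healing as "PWAT score of 0 for all subscores except subscore 8, where a score of up to 2 can be permissable". It adds that this is the stage at which nurses would leave a dressing on for a week. At completion the nurses are to "Photograph initial pressure injury and any remaining pressure injuries as per study recommendations". Step 17 is "Scoring of remaining photographs (see Assessment of wound photograph)", and step 18 closes participation and collects the study surface.

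The Wound Care section gives another rule. Once visits are weekly, "the wound is considered almost healed as per the RevPWAT (score <2) and thus endpoint for the study".

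Appendix B scores 0 on the size item when the "wound is closed (skin intact) or nearly closed", the second meaning under 0.3 cm². The other wound items carry the same allowance.

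The Statistical Analysis table compares healing times and also the number of injuries not healed at 8 weeks.

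**The concern.** The RevPWAT is scored photograph by photograph, so one qualifying photograph satisfies the Appendix A definition. The protocol then arranges what a confirmation would need: a second photograph of the same injury a week later, scored by assessors blinded to mattress. It does not say that this score must still qualify, what happens if it does not, or which date is the healing date.

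Two kinds of case can therefore enter the primary outcome as healed: a wound scored as closed too early, and a wound that closed and is open again at one week. The second bears directly on a comparison of support surfaces, because eligibility requires that the participant cannot reposition off the injury. Both cases also lower the count not healed at 8 weeks. After closure no further photographs are planned, so an analysis plan could reclassify such a case but could not recover its true healing date.

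**Working it through.** The protocol states no error or reopening rate, so there is no figure to reproduce. The check compares the sections and then sizes the issue under labelled assumptions.

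**1. The two endpoint rules**

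| | Appendix A | Wound Care |
|---|---|---|
| Threshold | subscores 1–7 = 0, subscore 8 ≤ 2 | score < 2 |
| When participation ends | one week after the threshold | at the weekly-visit stage |
| Later photograph | yes, and scored | none described |
| Effect of a later open wound | not stated | not applicable |

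Reading the Wound Care score as the total, a wound with subscores 1–7 at 0 and subscore 8 at 2 totals 0 + 2 = 2. It is healed under Appendix A and fails the Wound Care threshold. A confirming photograph exists only under Appendix A.

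**2. How easily one score could qualify**

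Grade 2 wounds are defined in Information Box 1 as having no slough, so the two necrotic-tissue items may be 0 from baseline. The remaining items among 1–7 (size, depth, granulation type and amount, edges) each give 0 below 0.3 cm². One misjudged area can therefore set all five to 0 together.

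**3. Premature dating, illustration only**

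Assume k photographs before true closure, a constant chance f that each wrongly qualifies, and a chance c that the one-week photograph also wrongly qualifies. None of these is in the documents.

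- Single photograph: 1 − (1 − f)^k
- With confirmation: 1 − (1 − f·c)^k

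| k = 8 | f = 1% | f = 2% | f = 5% |
|---|---|---|---|
| Single photograph | 1 − 0.99^8 = 7.7% | 1 − 0.98^8 = 14.9% | 1 − 0.95^8 = 33.7% |
| Confirmed, independent errors (c = f) | 0.08% | 0.32% | 2.0% |
| Confirmed, correlated errors (c = 0.5) | 3.9% | 7.7% | 18.3% |

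For the single-photograph rule, k = 4 gives 3.9%, 7.8% and 18.5%, and k = 12 gives 11.4%, 21.5% and 46.0%. The confirmed rows take every premature score to fall more than a week before true closure. A score less than a week early would be confirmed by a truly closed wound, leaving a dating error of under a week.

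**4. Reopening within the week, illustration only**

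Of the 60 final participants, assumed rates of 2%, 5%, 10% and 20% give 1.2, 3, 6 and 12. These are upper figures, because only participants recorded as healed can reopen.

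**5. Direction**

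Suppose a fraction p in each arm receives a date unrelated to the mattress. A true mean difference Δ becomes (1 − p)Δ, for example 0.851Δ at p = 14.9%. If instead the same fraction in each arm is dated early by the same number of days, Δ is unchanged. With 30 per group the standard error is SD × √(2/30) = 0.258 SD, so misdating that increases the spread widens the interval. The net effect is not determined.

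**The case against.** The strongest reply is that Appendix A ties the healed score to the weekly-dressing stage, so a stray low score during every-second-day dressings would not fit the description. That stands in part: errors should cluster late, when the wound is small, and move the date by days. A constant f over eight photographs therefore probably overstates the problem. It does not deal with a wound open again at one week, and the Wound Care section describes the weekly stage as almost healed only.

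The scoring step that step 17 refers to is not legible in the text at hand, and the flowchart is not shown. Either might describe several raters or adjudication. The legible healing definition and completion rule nonetheless contain no confirmation over time.

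It may also be said that dating an event from serial scores belongs in the analysis plan. The protocol itself fixes the event and the end of follow-up, however, and those determine which photographs exist.

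Three stronger readings are tempting and unsupported. A reader might infer that the protocol declares reopened wounds healed; it has no rule either way. A reader might infer that the flaw favours the equivalence claim; step 5 shows that this does not follow. A reader might take the reported intraclass correlation of 0.89 as evidence of a particular false-healed rate; it measures agreement between bedside and photograph scores and yields no such rate. The planned reliability test on pilot photographs is a safeguard.

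**Conclusion.** The point holds as a weakness in the primary event definition. One qualifying score establishes complete healing, and the one-week photograph, although taken and scored, cannot on the legible text confirm or overturn it. Healing time and the 8-week count are both affected.

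The documents do not allow the size or direction of the bias to be derived. The percentages above rest on assumed error rates, photograph numbers and error correlation. They show only that a single-photograph rule accumulates premature calls, and that confirmation reduces them greatly if errors are independent and by about half if c = 0.5. Confirmation would also not prove full closure, because a score of 0 admits an open wound under 0.3 cm². The change is worth making because the confirming photograph and its scoring are already planned.

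**What to change.** Define the primary event as the healed criterion met on one photograph and still met, on blinded scoring, on the planned one-week photograph. Date it at the first of the two. Score the one-week photograph before recording the participant as healed.

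Count unconfirmed cases as not healed. Continue photographic outcome follow-up for them to the existing maximum where possible, and otherwise censor at the last photograph. Apply the same definition to the count not healed at 8 weeks.

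Reconcile the Wound Care section with the completion step in Appendix A on both the threshold and the moment participation ends. How long the study mattress and wound care continue is for the investigators to settle.

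The cost is protocol wording, prompter scoring of a photograph already taken, and some extra outcome follow-up for unconfirmed cases. No stated sample size changes.
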